4.7.6.2 CCI

For the CCI the following weights will be calculated:

- CCI

Each domain score will be calculated as follows:

- CCI

The total score will be calculated as follows:

- CCI

Missing data will be dealt with as described in CCI

Weights of each item and other details for calculation are reported in CCI

The CCI and CCI (CCI) assessed at Visits 3 - 7 (End of Treatment) will be summarised by treatment group using descriptive statistics including 25th and 75th percentiles. Visit 7 for completed subjects only and Visit 7/EOT will be presented separately. Results for absolute changes from baseline will also be reported. Due to CTP amendments and to the corresponding changes in the procedures schedule, not all the subjects have undergone the same sequence of assessments. All the values collected will be summarised jointly. Considering the presence of a stratified and permuted blocks randomisation list no imbalance between treatments is expected.

Change from baseline in CCI total score at Visit 3, Visit 4, Visit 5, Visit 6 and Visit 7 (completed subjects only) and Visit 7/EOT will be analysed using a linear mixed model for repeated measures including treatment, visit, treatment-by-visit interaction, use of stable concomitant therapy with oral macrolides and country, as detailed in Section 4.9.1, as fixed effects and baseline value as covariate. An unstructured covariance matrix will be assumed and the Kenward-Roger adjustment will be used for the degrees of freedom. The least square means in each treatment group, the least square mean differences between treatments, their 95% CIs

CONFIDENTIAL

Sponsor:	Zambon S.p.A.	Protocol Number:	Z7224L02
----------	---------------	------------------	----------

and associated p-values overall and at each visit will be estimated by the model. The OBSMARGINS option will be used.

The above summaries/analyses will be performed using the mITT and PP Populations. Results for the PP Population will be considered as supportive.

Notes:

- While for Visit 2, Visit 4, Visit 5, Visit 6 and Visit 7 the 3-month version of the CCI is used, for Visit 3, data are collected for the 4-week version. Visit 2 scores will not be included in the linear mixed model analysis but they will be included in the descriptive analysis.

4.7.6.3 CCI

Summary statistics of the CCI and absolute change from baseline will be provided by treatment group for each trial visit.

Due to CTP amendments and to the corresponding changes in the procedures schedule and due to differences in the schedule of assessments in the local versions of the CTP, not all the subjects have undergone the same sequence of laboratory assessments. All the values collected will be summarised jointly. Considering the presence of a stratified and permuted blocks randomisation list no imbalance between treatments is expected.

The CCI as determined by the CCI (Visit 2) to Day 28 (Visit 3) and Visit 7 for completed subjects only and Visit 7/EOT will be compared between the treatment groups by a linear mixed model for repeated measures including treatment, country, as detailed in Section 4.9.1, and use of stable concomitant therapy with oral macrolides as fixed effects and baseline value as covariate. Least square means in each treatment group, least square mean difference between treatments, their 95% CIs and associated p-value will be estimated. OBSMARGINS option will be used for least square means estimates.

The analysis of covariance model will include only complete cases. CCI analysis might be added during the blind review meeting.

The above summaries/analyses will be performed using the mITT Population.

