Procedures performed at all clinical visits will include documentation of concomitant medications and treatment emergent adverse events (TEAEs) as well as spirometry to determine forced expiratory volume in 1 second (FEV₁) and forced vital capacity (FVC). Additionally, the subjects will be asked by the Investigator for information on any NCFB pulmonary exacerbations that were not reported.

Further CCI samples will be collected at Visits 2, 3, 5 and 7 to be analysed CCI. CCI samples collected at Screening (Visit 1) and at the end of treatment (Visit 7) will have isolates retained by the central laboratory for later analysis CCI.

At Visits 2, and at each post-baseline study visit, CCI will be assessed using the CCI.

In case subjects feel that they are experiencing a NCFB pulmonary exacerbation (as defined in [Section 19.2](#)), they should contact the investigational site immediately to discuss their symptoms and, if feasible, to arrange an Exacerbation Visit (which should take place within 2 working days of the exacerbation starting, if possible). The Investigator will check whether the pulmonary exacerbation meets the criteria defined in this Clinical Trial Protocol (CTP) and will decide on an appropriate course of action (including systemic antibiotic treatment, if required).

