Subsequently, CCI (5 mL) will be collected at each visit with the exception of Visits 4 and 6 as well as at any Exacerbation Visit (including episodes of pneumonia), if feasible. Two samples may be taken during the clinic visit or at home on the morning of the visit, with the CCI only being sent for analysis. They will be sent refrigerated on the day of collection for analysis to CCI or CCI, specialized in microbiological analyses. CCI will be responsible for all aspects of the CCI analyses, including preparation of laboratory kits to be provided to investigational sites and will perform laboratory data management activities.

For analysis of CCI, these CCI will be collected in sterile transport tubes and shipped refrigerated to the microbiological laboratory by selected courier to preferably arrive at the laboratory within 48 hours after collection. Results of this quantitative analysis for CCI will be presented as colony forming units (CFU) count per millilitre. Additionally, results from Visit 1 (Screening) and Visit 7 (End of Treatment) will be made available to the Investigator in the form of laboratory reports via fax/email for the subjects' following visit/contact and transferred to the trial database according to pre-defined criteria. Results from other visits will not be reported directly to the Investigator in order not to bias safety and efficacy evaluations. The CCI will also be evaluated at specific visits (see [Section 10.1.6](#)).

More details on laboratory analyses and logistics can be found in the laboratory manual.

CCI Download

The subjects will administer the IMP via the CCI device twice daily which is activated by a disc provided with the CCI. Subjects will receive appropriate training on the use of the CCI device (including written instructions) and on preparation of the IMP to be used in the CCI. Subjects will perform the first administration of IMP under supervision of the site personnel during Visit 2 and they will be informed that the device will log their IMP usage. When subjects self-administer the IMP via the CCI device, the time of day, length of nebulisation and amount of IMP administered are stored in the device.

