 The CCI [REDACTED] as determined by the mean change in CCI [REDACTED] from baseline (Visit 2) to Day 28 (Visit 3), as well as to Visits 5 and 7, will be compared between the treatment groups by an analysis of covariance model including treatment, pooled site and use of stable concomitant therapy with oral macrolides as fixed effects and baseline value as covariate. Least square means in each treatment group, least square mean difference between treatments, their 95% CIs and associated p-values will be estimated.

CCI [REDACTED] analyses may be conducted to assess the robustness of conclusions.

Summary statistics of the CCI and change from baseline (Visit 2) will be provided by treatment group for each trial visit.

CCI

Absolute and relative frequency of subjects CCI for CCI will be presented by treatment group along with the summaries for the CCI. Total number of CCI due to CCI per follow-up month will be collected during the study and described by treatment group.

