4.11 Missing Data

The validity of the negative binomial model planned for the primary efficacy analysis of the mean annual CCI [REDACTED] relies on the MAR assumption. CCI [REDACTED] have been outlined in Section 4.7.4.2 of this SAP to investigate the robustness of the primary endpoint conclusion under assumptions of MNAR.

CONFIDENTIAL

Sponsor:	Zambon S.p.A.	Protocol Number:	Z7224L02
----------	---------------	------------------	----------

In the analysis of CCI total score, CCI domain scores and CCI CCI linear mixed models for repeated measures will be used to handle missing data. Under the MAR assumption, these models provide an unbiased estimate of the treatment effect that would have been observed if all subjects had continued on treatment [7].

CCI analyses might be added during the blind review meeting if the amount of missing data makes it reasonable for further investigations of their influence on the overall study results. Decisions will be documented in the Blind Data Review and Analysis Sets Report.

Unless stated otherwise, there will be no imputation of missing values and only observed data will be included in the summaries.

The number of subjects with missing data will be presented under a “Missing” category. Unless otherwise stated, missing values will be included in the denominator count when computing percentages.

When continuous data are being summarised, only the non-missing values will be evaluated for computing summary statistics.

In order to calculate the duration of last usage of colistimethate sodium/colistin and the time from last administration of colistimethate sodium/colistin, the following rules will be applied for partial dates of start and stop date of last administration of colistimethate sodium/colistin:

For the start date:

- if only the day is missing, the first day of the month will be assumed;
- if the day and the month are missing, then the date will not be imputed and the time/duration will be classified as “Not Evaluable”.

For the stop date:

- if only the day is missing, the last day of the month will be assumed;
- if the day and the month are missing, then the date will not be imputed and the time/duration will be classified as “Not Evaluable”.

Where a medication start date is partially or fully missing, and it is unclear as to whether the medication is prior or concomitant, it will be assumed that it is concomitant.

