4.13 Changes in Conduct or Planned Analyses from the Protocol

Sections 2.2, 4.4.11, 4.7.5 and 4.7.6.3: The protocol incorrectly referred to the units for the determination of CCI CCI which have been reported as CCI by the central laboratory.

Section 4.7.4: The protocol states that the Negative Binomial Model will consider the log-time on study as offset. However, as specified in Section 4.1.7, NCFB Pulmonary Exacerbations analyses focus on the treatment period so log-time on treatment will be considered.

Sections 4.7.5 and 4.7.6.1: The protocol states that the CCI
[REDACTED]
[REDACTED]. Using date of first IMP as the start time of risk is considered to be biased, so date of randomisation will be used instead.

CONFIDENTIAL

Sponsor:	Zambon S.p.A.	Protocol Number:	Z7224L02
----------	---------------	------------------	----------

Section 4.7.6.1: The protocol states that the CCI [REDACTED] CCI [REDACTED] For time-to-event endpoints, generally the + 1 is not included because this overestimates the time by 1 day for every event, therefore “+ 1” has been deleted.

Section 4.7.6.5: The protocol states that the CCI [REDACTED] total score will be computed and analysed. However, as recommended in the Manual Scoring Instructions [REDACTED], only the CCI [REDACTED] domain scores will be presented and analysed.

There have been no other changes in analyses from those defined in the protocol.

CONFIDENTIAL

Sponsor:	Zambon S.p.A.	Protocol Number:	Z7224L02
----------	---------------	------------------	----------

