5.3.3 Section 14.2: Secondary

Table 14.2.2.1.1	CCI : Kaplan-Meier Estimates	(mITT Population)
Table 14.2.2.1.2	CCI : Kaplan-Meier Estimates	(PP Population)
Table 14.2.2.1.5	CCI : Weibull Accelerated Failure Time Model	(mITT Population)
Table 14.2.2.1.6	CCI : Weibull Accelerated Failure Time Model	(PP Population)
Table 14.2.2.2.1	CCI : Cox proportional hazard regression model	(mITT Population)
Table 14.2.2.2.2	CCI : Cox proportional hazard regression model	(PP Population)
Table 14.2.2.2.3	CCI : Cox proportional hazard regression model - CCI Analysis for the Effect of Concomitant Antibiotic Therapy	(mITT Population)

CONFIDENTIAL

Sponsor:	Zambon S.p.A.	Protocol Number:	Z7224L02
----------	---------------	------------------	----------

Table 14.2.2.2.4	CCI [REDACTED]: Cox proportional hazard regression model - CCI [REDACTED] Analysis for the Effect of Concomitant Anti-Pseudomonal Antibiotic Therapy	(mITT Population)
Table 14.2.2.3	CCI [REDACTED]: Kaplan-Meier Estimates by IMP Adherence	(mITT Population)
Table 14.2.2.5.1	CCI [REDACTED]: Domain Scores and Total Score Results and Change Versus Baseline	(mITT Population)
Table 14.2.2.5.2	CCI [REDACTED]: Domain Scores and Total Score Results and Change Versus Baseline	(PP Population)
Table 14.2.2.5.3	CCI [REDACTED]: Linear Mixed Model for Repeated Measures for Change from Baseline in Total Score	(mITT Population)
Table 14.2.2.5.4	CCI [REDACTED]: Linear Mixed Model for Repeated Measures for Change from Baseline in Total Score	(PP Population)
Table 14.2.2.6.1	CCI [REDACTED] Density: Results and Change from Baseline	(mITT Population)
Table 14.2.2.6.2	CCI [REDACTED] Density: Linear Mixed Model for Repeated Measures for Change from Baseline at Visit 3, Visit 7 and End of Treatment	(mITT Population)
Table 14.2.2.7.1	Severe CCI [REDACTED]: Mean Annual Rate by Negative Binomial Model	(mITT Population)
Table 14.2.2.7.2	Time to CCI [REDACTED] Exacerbation: Kaplan-Meier Estimates	(mITT Population)
Table 14.2.2.8.1	CCI [REDACTED] - CCI [REDACTED] Days: Summary Statistics	(mITT Population)
Table 14.2.2.8.2	CCI [REDACTED] CCI [REDACTED] Days: ANCOVA model	(mITT Population)
Table 14.2.2.9	CCI [REDACTED]	(mITT Population)
Table 14.2.2.10.1	CCI [REDACTED]	(mITT Population)
Table 14.2.2.10.2	CCI [REDACTED]: Mean Annual Rate by Negative Binomial Model	(mITT Population)
Table 14.2.2.11.1	CCI [REDACTED]: Domain Scores Results and Change Versus Baseline	(mITT Population)

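### The SAP's model for the sputum endpoint drops the protocol's Visit 5 comparison between arms without declaring it, and SAP 4.13 states that nothing else changed

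*SAP*

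**What the plan says.** The endpoint's name is blacked out. The visit schedule, the word density in the titles of Tables 14.2.2.6.1 and 14.2.2.6.2, and the central-laboratory units mentioned in SAP 4.13 identify it as the sputum bacterial density endpoint.

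- **Collection.** Protocol 7.1 says that "samples will be collected at Visits 2, 3, 5 and 7 to be analysed". Protocol 10.1.5 says that the material "will be collected at each visit with the exception of Visits 4 and 6". Footnote d of the flow chart (Protocol Appendix 1, SAP 3.3.1) keeps Visit 5, and so does the French chart in SAP 3.3.2.
- **Protocol analysis.** Section 19.4.2 specifies an analysis of covariance in which the change "from baseline (Visit 2) to Day 28 (Visit 3), as well as to Visits 5 and 7, will be compared between the treatment groups", with least-squares mean differences, intervals and p-values.
- **SAP analysis.** Section 4.7.6.3 uses a linear mixed model for repeated measures and compares the arms at "Visit 2) to Day 28 (Visit 3) and Visit 7 for completed subjects only and Visit 7/EOT will be compared between the treatment groups". Table 14.2.2.6.2 is titled "Linear Mixed Model for Repeated Measures for Change from Baseline at Visit 3, Visit 7 and End of Treatment". The terms listed in 4.7.6.3 and 4.9 are treatment, country, macrolide use and baseline. No visit or treatment-by-visit term is listed.
- **Missing data.** Section 4.11 says of this group of endpoints that "linear mixed models for repeated measures will be used to handle missing data". Section 4.7.6.3 says that an analysis of covariance model is limited to complete cases.
- **Declared changes.** The only SAP 4.13 entry that cites 4.7.6.3 concerns units. The section ends: "There have been no other changes in analyses from those defined in the protocol".

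**The concern.** A comparison planned in the protocol, on data that are collected, has no counterpart in the SAP's model or its table, and the section meant to list such changes says there are none. A reader cannot tell an intended omission from an oversight.

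The early stop makes the loss more relevant. Recruitment ended in November 2021 with 287 of 420 subjects randomised, and everyone was to return by the end of February 2022 (SAP 3.9). Of the two late comparisons left, one is restricted to completers. The other, Visit 7/EOT, can mix treatment durations, because SAP 4.1.10 assigns early-termination visits to Visit 7. Visit 5 is the only scheduled sputum sample between Day 28 and month 12, and more subjects could reach it than could reach month 12. As the SAP stands, it gets no modelled difference, interval or p-value.

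Visit 5 is also the last scheduled sample before Visit 7. Leaving it out of a model that is meant to handle missing data could cost the Visit 7 estimate some precision.

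**Working it through.** The plan gives no sample size, standard deviation or power for this endpoint, so there is no figure to reproduce.

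**1. Is redaction the explanation?** No. The visits in SAP 4.7.6.3 and in the table title are legible and agree. The section references that open each 4.13 entry are also legible. Only one cites 4.7.6.3, and its subject is units. The neighbouring model in 4.7.6.2 covers Visits 3 to 7 with visit and treatment-by-visit terms, so the SAP's general approach does not explain the gap either.

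**2. How many subjects could reach month 6 but not month 12?** From the SAP: 287 randomised, recruitment stopped in November 2021 (3.9), closure on 28 February 2022 (4.7.4.2). Assumed: uniform accrual, first randomisation between 15 January and 30 June 2018, last between 1 and 30 November 2021. Visit windows are ignored.

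A subject has fewer than 365 days to closure if randomised on or after 1 March 2021, and fewer than 183 days if randomised on or after 30 August 2021. Number affected = 287 × days in that window / total accrual days.

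- Cannot reach month 12: 287 × 246/1387 = 51 to 287 × 275/1250 = 63.
- Cannot reach month 6: 287 × 64/1387 = 13 to 287 × 93/1250 = 21.
- Can reach month 6 but not month 12 (182 days of accrual): 287 × 182/1416 = 37 to 287 × 182/1221 = 43.

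**3. What would a Visit 5 contrast detect?** With two-sided 0.05, 80% power and n per arm, the detectable difference in residual SDs is (1.96 + 0.84) × √(2/n). If 70% of 287 are observed, n = 100 and the result is 0.40. If all are observed, n = 143.5 and the result is 0.33.

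**4. What does omitting Visit 5 do to the Visit 7 contrast?** Assumed: likelihood fit to all available data; Visit 7 missing in a share m of 10–40%; Visit 5 observed in 50–100% of those; correlation 0.3–0.8, either equal between visits or decaying per 6 months. When Visit 5 is always observed, the variance is proportional to

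V = (1 − R²)/(1 − m) + R²,

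where R² is the share of Visit 7 variance explained by the earlier visits in the model.

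Example with decaying correlation 0.7 and m = 0.20. With Visit 3 only, R² = (0.7^(11/6))² = 0.2704 and V = 0.7296/0.8 + 0.2704 = 1.1824. With Visits 3 and 5, R² = 0.49 and V = 0.51/0.8 + 0.49 = 1.1275. The ratio is 1.049, so the standard error is 2.4% larger without Visit 5.

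Full grid:

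| Visit 7 missing | Variance ratio, without / with Visit 5 | Standard error larger by |
|---|---|---|
| 10% | 1.003–1.023 | 0.1–1.2% |
| 20% | 1.006–1.049 | 0.3–2.4% |
| 30% | 1.009–1.077 | 0.4–3.8% |
| 40% | 1.013–1.109 | 0.6–5.3% |
| complete cases only | 1.000 | 0 |

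**5. Bias.** A simulation with 400,000 per arm set the true Visit 7 difference at −0.40 SD and let 14–22% drop out depending on their Visit 5 value. The estimate was −0.397 to −0.405 with Visit 5 in the model and −0.382 to −0.396 without it, a shift of about 0.02 SD or less.

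**The case against.** The strongest reply is that this is a documentation mismatch on one secondary endpoint. Several parts of that reply stand.

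- A reader might infer that the 6-month result is lost. It is not: SAP 4.7.6.3 gives summary statistics and change from baseline by arm at each trial visit, and Table 14.2.2.6.1 and Figure 14.2.2.6.3 remain. Only the modelled contrast, its interval and its p-value are dropped.
- A reader might infer that the end-of-treatment estimate is materially weakened. The grid does not support that, and if the complete-case sentence in 4.7.6.3 is applied literally, the loss is nil. Where an early-termination sample exists, Visit 7/EOT is observed, so nothing has to be predicted from Visit 5.
- A reader might infer that the early closure puts the missing-at-random assumption at risk. The subjects cut off administratively miss month 12 because of their randomisation date, not their sputum results. Only true drop-outs bear on that assumption.
- The secondary endpoint wording (SAP 2.2) and the testing order (4.7.5) are blacked out, so whether Visit 5 was ever a tested time point cannot be checked.

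None of this answers the main point. The protocol plans a comparison at Visit 5, the SAP omits it, and the visible text of 4.13 does not say so.

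**Conclusion.** The point holds as an undeclared departure from the protocol. The Visit 5 difference, interval and p-value have been removed, the method has moved from ANCOVA to a repeated-measures model, and the closing statement of SAP 4.13 is wrong on both counts. This rests on legible text.

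The early stop gives Visit 5 some added value: about 37–43 of 287 subjects could supply a 6-month but not a 12-month sample. That range depends on uniform accrual, which the documents do not establish. It should not be read as saying that month 12 is out of reach for most: on the same assumption, 224–236 subjects could reach month 12 and 266–274 could reach month 6, before drop-out.

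The gain for Visit 7 is a minor benefit: 0.3–2.4% in standard error at 20% missing (about the planned drop-out rate), about 5% at the extreme, and none with complete cases. The correlations and missing shares are assumptions. The documents do not show whether the omission was deliberate.

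Two faults in the same section limit what restoring Visit 5 alone would achieve. Without a visit or treatment-by-visit term, the model as listed yields one average treatment difference. The complete-case sentence also contradicts 4.11.

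**What to change.** - In SAP 4.7.6.3 and 4.9, add Visit 5 as an outcome visit and list visit and treatment-by-visit as model terms for this endpoint.
- In 4.14, rewrite the contrasts for Visits 3, 5 and 7. The example code already has the two visit terms, but its contrasts cover Visits 4 to 7, which is not the sputum schedule.
- Add the Visit 5 difference with its confidence interval to Table 14.2.2.6.2, next to the results already planned.
- Remove the complete-case sentence, or reconcile it with 4.11.
- Leave the tested time point in the 4.7.5 hierarchy unchanged, so that no new multiplicity question arises.
- In 4.13, list the change of method for this endpoint. If dropping Visit 5 was intended, state that and the reason there, and correct the closing statement.

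The cost is wording, a few lines of code and one table row. No new data are needed.

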4.9 Adjustment for Covariates

The adjusted mean annual NCFB pulmonary exacerbation rate will be estimated by a negative binomial model including treatment, use of stable concomitant therapy with oral macrolides (e.g. azithromycin or erythromycin or clarithromycin: Yes/No) and country, as detailed in Section 4.9.1, as fixed effects and log-time on treatment as an offset. An exploratory model will also be fitted considering the number of CCI requiring oral/intravenous antibiotics in the last 12 months prior to study entry.

The Cox proportional hazard regression model for CCI will include use of stable concomitant therapy with oral macrolides (e.g. azithromycin or erythromycin or clarithromycin: Yes/No) and country, as covariates.

In the analysis of CCI total score and CCI domain scores, a linear mixed model for repeated measures will be applied. This will include treatment, visit, treatment-by-visit interaction, use of stable concomitant therapy with oral macrolides (e.g. azithromycin or erythromycin or clarithromycin: Yes/No) and country, as fixed effects and baseline value as covariate.

The CCI CCI will be analysed by means of a linear mixed model for repeated measures including treatment, country, and use of stable concomitant therapy with oral macrolides (azithromycin or erythromycin or clarithromycin: Yes/No) as fixed effects and baseline value as covariate.

CONFIDENTIAL

Sponsor:	Zambon S.p.A.	Protocol Number:	Z7224L02
----------	---------------	------------------	----------

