- EoT should be replaced by the last time (in days) to event >270 days (if any);

• **Tables that require Cox proportional hazards model and 95% CIs of hazard ratios between treatments:**

PROC PHREG data=dset;
CLASS treatment psite med;
*MODEL time*event(1) = treatment psite med / ties=exact;*
HAZARDRATIO 'Col. Sodium vs Placebo' treatment / cl=both;
BY byvar; (optional)
WHERE wherever; (optional)

RUN;

Notes:

- Psite represents the country, as detailed in Section 4.9.1;
- Med represents use of stable concomitant therapy with oral macrolides (e.g. azithromycin or erythromycin or clarithromycin) (Yes/No);
- Time represents the time to event or time to censoring;
- Event represents the censoring indicator (1 = censored);
- If the option ties=exact requires a considerable amount of computer resources, the Efron approximation will be used (*ties=efron*).
- Treatment order: 1= Colistimethate Sodium, 2= Placebo.

CONFIDENTIAL

Sponsor:	Zambon S.p.A.	Protocol Number:	Z7224L02
----------	---------------	------------------	----------

- **Tables that require negative binomial modelling, including 95% CIs of treatment ratios:**

```
PROC GENMOD data = dset;
  CLASS treatment psite med;
  MODEL count = treatment psite med / offset=log_years link=log dist=negbin wald
  type3;
  ESTIMATE 'Col. Sodium / Placebo' treatment 1 -1 / exp;
  lsmeans treatment / ilink cl diff exp om;
  BY byvar; (optional)
  WHERE wherever; (optional)
RUN;
```

Notes:

- Psite represents the country, as detailed in Section 4.9.1;
- Med represents use of stable concomitant therapy with oral macrolides (e.g. azithromycin or erythromycin or clarithromycin) (Yes/No);
- Count represents the total number of exacerbations for each patient;
- log_years represents the logarithm of the follow-up time in years;
- Treatment order: 1= Colistimethate Sodium, 2= Placebo.

- **Tables that require linear mixed model for repeated measures and 95% CIs of differences between treatments:**

```
PROC MIXED data = dset;
  CLASS treatment visit psite med sub;
  MODEL change = treatment visit treatment*visit psite med baseline/ s ddfm=kr;
  REPEATED visit / subject=sub type=un r;
  LSMEANS treatment treatment*visit / om at means cl slice=visit;
  LSMESTIMATE treatment
  'Col. Sodium / Placebo' 1 -1 / cl;
  LSMESTIMATE treatment*visit
  'Col. Sodium / Placebo: Visit 4' 1 0 0 0 -1 0 0 0,
  'Col. Sodium / Placebo: Visit 5' 0 1 0 0 0 -1 0 0,
  'Col. Sodium / Placebo: Visit 6' 0 0 1 0 0 0 -1 0,

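### SAP 4.7.6.3 and 4.9 omit visit and treatment-by-visit from the sputum-density repeated-measures model, in conflict with the SAP's own code and with the by-visit table it plans

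*SAP*

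**What the plan says.** The endpoint's name is redacted in SAP 4.7.6.3. The unredacted word Density in the titles of Tables 14.2.2.6.1 and 14.2.2.6.2, together with the sputum schedule, identifies it.

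- **SAP 4.7.6.3, timepoints.** Changes from Visit 2 "to Day 28 (Visit 3) and Visit 7 for completed subjects only and Visit 7/EOT will be compared between the treatment groups".
- **SAP 4.7.6.3, model.** A "linear mixed model for repeated measures including treatment, country, as detailed in Section 4.9.1, and use of stable concomitant therapy with oral macrolides"; baseline is the only other term listed. The output is a "least square mean difference between treatments, their 95% CIs and associated p-value will be estimated": one difference and one p-value, with no mention of results by visit.
- **SAP 4.7.6.3, a later sentence.** It calls the same analysis an analysis of covariance restricted to complete cases.
- **SAP 4.9.** The model is given again as a "linear mixed model for repeated measures including treatment, country, and use of stable concomitant therapy with oral macrolides", with baseline.
- **SAP 4.7.6.2, for comparison.** The questionnaire total score has a "linear mixed model for repeated measures including treatment, visit, treatment-by-visit interaction, use of stable concomitant therapy with oral macrolides and country", with results overall and at each visit. The domain-score model in 4.7.6.9 is built the same way.
- **SAP 4.14.** The only code for tables needing a repeated-measures mixed model has "MODEL change = treatment visit treatment*visit psite med baseline/ s ddfm=kr" and "LSMEANS treatment treatment*visit / om at means cl slice=visit", with unstructured covariance.
- **SAP 5.3.3.** Table 14.2.2.6.2 uses the repeated-measures model name and is titled for Visit 3, Visit 7 and End of Treatment.
- **Protocol 19.4.2.** An analysis of covariance in which changes "from baseline (Visit 2) to Day 28 (Visit 3), as well as to Visits 5 and 7, will be compared between the treatment groups".

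**The concern.** A repeated-measures model with neither a visit term nor a treatment-by-visit term forces the same mean change at every visit within an arm and one constant treatment difference. It has no parameter for the Day 28 effect or for the end-of-treatment effect, yet both comparisons are promised. For an inhaled antibiotic, an early fall in density that wanes by month 12 is a natural question, and here the p-value would test neither timepoint.

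The omission appears in both sections that describe the model. In 4.9 it stands next to questionnaire models that do list the two terms. The output wording, one difference and one p-value, fits the shorter model. A programmer working from the section text and one working from the code would produce different analyses of a secondary endpoint.

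**Working it through.** The documents give no effect size, variance or power figure for this endpoint, so there is no planned figure to reproduce. The check has two parts.

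**1. Which analysis do the documents specify?**

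| Source | Visit terms | Output |
|---|---|---|
| SAP 4.7.6.3, model sentence | none | one difference, one p-value |
| SAP 4.7.6.3, complete-case sentence | none needed if ANCOVA is fitted per visit | not stated |
| SAP 4.9 | none | not stated |
| SAP 4.14 mixed-model code | visit and treatment*visit | contrasts at Visits 4, 5, 6, 7 |
| SAP Table 14.2.2.6.2 title | implied | Visit 3, Visit 7, End of Treatment |

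The code does not settle the matter. The flow chart in SAP 3.3.1 and Protocol 10.1.5 place no sputum sample at Visits 4 and 6. The contrasts carry four coefficients per arm, for four visits, and none is for Visit 3. They cannot be run as written on the sputum visits.

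**2. What does the section text estimate if fitted to stacked visits?**

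Assumptions, none from the documents unless stated:
- Two visits (Visit 3 and Visit 7), log10 scale, covariance taken as known.
- SD 2 at each visit; correlation r of 0.3, 0.5 or 0.7.
- Fraction d missing at Visit 7, completely at random and equal in both arms: 0, 0.2 or 0.4. SAP 3.9 assumes about 20% drop-out.
- True treatment differences of -1.5 at Visit 3 and -0.5 at Visit 7.

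With equal SDs, generalised least squares gives Visit 3 the weight

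w3 = [(1-d)/(1+r) + d] / [2(1-d)/(1+r) + d],

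and the estimate is -1.5·w3 - 0.5·(1-w3) = -0.5 - w3.

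- d = 0: w3 = 0.50 for any r, estimate -1.00.
- d = 0.2, r = 0.5: w3 = (0.533 + 0.2)/(1.067 + 0.2) = 0.579, estimate -1.08. Over r = 0.3 to 0.7: -1.07 to -1.09.
- d = 0.4, r = 0.5: w3 = (0.4 + 0.4)/(0.8 + 0.4) = 0.667, estimate -1.17. Over r = 0.3 to 0.7: -1.15 to -1.18.

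With r = 0.5 and d = 0.2 but unequal SDs at Visits 3 and 7, the estimate is -1.44 for SDs of 1.5 and 2.5, and -0.65 for SDs of 2.5 and 1.5.

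With visit and treatment-by-visit included, the model returns -1.5 and -0.5 in every equal-SD scenario. If the true effect is -1.0 at both visits, both models return -1.0.

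**Precision cost of the fuller model** (r = 0.5, d = 0.2, 143 per arm from 287 randomised):
- Pooled SE = sqrt[2·4/(143·1.267)] = 0.210.
- Visit 3 SE = sqrt(2·4/143) = 0.237.
- Visit 7 SE = sqrt[2·(4/143)·(0.25 + 0.75/0.8)] = 0.258.

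**The case against.** The strongest reply is that no pooled model is settled. The SAP's only repeated-measures code has both terms, and the planned table is titled by visit. The fixed effects in 4.7.6.3 match the protocol's ANCOVA, with country in place of pooled site, and they match the ANCOVA code in 4.14, which has an optional BY statement. With the surviving complete-case sentence, this looks like ANCOVA wording left under a new model name. A separate ANCOVA at each timepoint needs no visit term. Visit 7 completers and Visit 7/EOT also overlap, so some separate fitting must be intended. All of this stands, and it makes the point a contradiction to resolve, not a wrong model already chosen.

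It does not close the matter. A per-visit ANCOVA on complete cases conflicts with the repeated-measures model named in 4.7.6.3 and 4.9, and with 4.11, which relies on mixed models to handle missing data for these endpoints.

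A reader might infer three stronger points that the documents do not support:

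- **That waning would be hidden.** SAP 4.7.6.3 requires descriptive statistics and changes from baseline at each visit, and Figure 14.2.2.6.3 plots change by visit. Only the inferential contrast is at issue.
- **That the pooled estimate is materially biased when the drug does nothing.** Assume a 1-log10 shift between visits, 35% against 15% missing, r = 0.5, SD 2 and 140 per arm. The Visit 7 weight (1 - w3) is 0.433/(0.867 + 0.35) = 0.356 in one arm and 0.567/(1.133 + 0.15) = 0.442 in the other. The bias is 0.085 against an SE of 0.214, or about 0.4 SE. Its sign depends on the assumed directions. It is zero if only subjects with both visits are used, because both arms then have the same weights.
- **That the SAP fails to name the tested timepoint.** The hierarchy in 4.7.5 and the endpoint definitions in 2.2 are redacted, so this cannot be judged.

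**Conclusion.** The inconsistency is real. The two sections that define the sputum-density model omit visit and treatment-by-visit and describe one difference and one p-value. The code has the terms but contrasts the wrong visits for sputum, and the table expects results that the written model cannot supply.

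Under the section text, assumed effects of -1.5 and -0.5 log10 become one value of about -1.0 to -1.2 with equal visit SDs, and -0.65 or -1.44 in the two unequal-SD cases. The weighting is then set by dropout and variance, not by a stated estimand. If complete cases means subjects with both visits, the equal-SD value is -1.00, still the effect at neither visit. These sizes rest wholly on assumed effects, SDs, correlations and missingness. The estimate misrepresents a visit only if the effect changes over time.

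This is a should-fix point on a secondary endpoint. It does not touch the primary analysis.

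**What to change.** 1. In SAP 4.7.6.3 and 4.9, add visit and treatment-by-visit, with unstructured covariance and Kenward-Roger degrees of freedom as for the questionnaires. Report the difference, CI and p-value at Visit 3 and at Visit 7.
2. State which visits enter the model, including whether Visit 5 does, since the protocol compares it and 4.7.6.3 does not list it.
3. Fit Visit 7 completers and Visit 7/EOT in separate models. They overlap and cannot both be levels of visit in one model.
4. In 4.14, give this endpoint its own contrasts for the sputum visits, including Visit 3.
5. Delete the complete-case ANCOVA sentence, or reconcile it with 4.11.
6. Confirm that the contrast used in the hierarchy is the one named in the redacted list in 4.7.5.

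The cost is SAP wording and a few lines of code, with no new data. The by-visit intervals are somewhat wider than the pooled one: in the illustration, 0.237/0.210 gives about 13% at Visit 3 and 0.258/0.210 about 23% at Visit 7.
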